Prior to conducting the primary analyses, group differences in baseline measures will be evaluated to ensure that the group assignment was even. We will also inspect the

distributions of continuous variables (e.g., frequency condom use) for departures from normality. Variables that exhibit non-normal distributions will be subjected to normalizing transformations prior to analysis. If those transformations are unsuccessful, analysis will proceed using non-parametric tools. In addition, the rate of attrition between baseline and follow-up interviews will be evaluated to ensure that it is relatively constant across intervention conditions, and that there are no systematic differences in the variables of interest between participants who completed the study and those lost to follow-up. Missing data due to item non-response or loss to follow-up will be handled using the most appropriate method, depending on the amount of missing data, the assumptions of the missing data (completely at random, at random or non-ignorable) and the assumptions of the method of handling missing data. For example, for small amounts of missing data that are assumed to be missing at random, listwise or pairwise deletion (the default in most statistical packages) will be sufficient. Variables that differ significantly between those who returned for follow-up and those who did not can also be controlled for in regression analyses. Where appropriate, we will use statistical models that employ maximum likelihood techniques of parameter estimation, allowing us to use participants with incomplete data and avoid the potential bias caused by listwise deletion. These techniques are robust under conditions of missing at random so comparisons of groups will not be biased as long as missing data is ignorable. The number of planned comparisons will be limited based on a priori hypotheses, therefore the per comparison error rate of .05 will be used to evaluate significance of the specific aims. Exploratory or secondary analyses will be adjusted for multiple comparisons using the Bonferroni test.

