Many of the variables will be either summary index scores or latent variables that assess the psychological, behavioral and biological constructs of interest. For example knowledge will be a summary score representing the number of variables the participant correctly endorsed, while motivation will be a mean score across multiple variables representing the underlying latent construct. The variable related to use of LARCs will be a dichotomous variable representing current use or no current use of a LARC method (IUD or Implanon), as will attending a family planning visit during the study period.

Separate analyses will be conducted for each of the hypothesis to understand differential change over time. This includes looking at change scores as well as analysis of variance. The expectations for hypotheses 1 and 2 are that they will significantly increase in the intervention group. Differences will be assessed from baseline to follow-up period for each analysis.

Additional regression analyses will be conducted to identify significant predictors of differential change over time in birth control method and family planning visit. This analysis will determine if the intervention condition is a significant predictor of change. The regressions will account for any important statistically significant differences between groups at baseline. These differences may include variables pertaining to demographics, psychosocial factors, and behavioral variables. Generalized estimated equations (GEE) will be used to account for the within-subject correlation of repeated measures by individual patients. Group designations for the outcome analyses will adhere to the intention to treat threshold. All Statistical analyses will be performed using SAS (version 9.1 or later, SAS Institute Inc, Cary, NC) software.

*Engagement variables.* We will collect and analyze engagement with the PN and attendance to each session. These analyses will be used to assess intervention fidelity and to describe the amount of intervention each participant received to understand acceptability of the intervention as well as the relationship of intervention dose to study outcomes. These data will include, intervention activities covered and descriptive information such as the number of sessions attended, and the number of interactions with

the PN.

We will also record intervention sessions with the PN to determine the fidelity in which each session has been administered.

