**Study Statistical Power.** Power analyses were done to assess the minimum detectable improvement needed for LARC uptake. A sample of 75 per group, using ITT approaches and assuming outcome if failure (dichotomous only) for patients who do not respond to follow-up surveys will provide 80% power to detect 23% difference between usual care and intervention patients on dichotomous outcomes, assuming an average success rate of 50% for maximum variability. For continuous outcomes, a follow-up sample size of 60 per group will provide 80% power to detect a .55 SD difference between usual care and intervention patients, or a medium linear effect over time (correlational structure CS with  $\rho=.5$ ).

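### The plan's assurance for incomplete data rests on likelihood models it never names; the only repeated-measures method it names is GEE, which is not generally valid under missing at random

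*Combined protocol and SAP*

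**What the plan says.** All of this is in section IV.F, Data Analysis Plan, of the combined protocol and SAP, unless another section is named.

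**Missing data.** The method is left open, to be chosen by the amount and type of missingness. Three options appear:
- For small amounts assumed MAR, "listwise or pairwise deletion (the default in most statistical packages) will be sufficient".
- Characteristics on which women lost to follow-up differ significantly from those retained may be adjusted for in the regressions.
- "Where appropriate, we will use statistical models that employ maximum likelihood techniques of parameter estimation". The assurance follows directly: "These techniques are robust under conditions of missing at random so comparisons of groups will not be biased", on condition that the missingness is ignorable.

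Attrition is also to be compared between arms, and completers are to be compared with women lost to follow-up.

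**Analyses named.** The hypotheses are to be examined with change scores and analysis of variance. Additional regressions are to "identify significant predictors of differential change over time in birth control method and family planning visit", and in that paragraph comes the GEE sentence: "Generalized estimated equations (GEE) will be used to account for the within-subject correlation of repeated measures by individual patients".

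**Power statement.** The dichotomous calculation uses 75 per group, "assuming outcome if failure (dichotomous only) for patients who do not respond to follow-up surveys". The continuous calculation uses 60 per group at follow-up and a compound-symmetry (CS) correlation of 0.5. Neither the failure rule nor the correlation structure is repeated as part of the analysis.

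**The concern.** The assurance of no bias belongs to likelihood models, but no analysis in the plan is committed to being one. GEE is not likelihood-based. On available data without weighting, it is guaranteed valid only when missingness is completely at random or depends only on covariates in the model. If a woman's 3-month answers affect whether she responds at 6 months, the data can be MAR and GEE can still be biased, by an amount that depends on a working correlation the plan does not state. Complete-case change scores have a similar weakness.

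Section IV.E calls retention the biggest potential scientific problem. Only one arm meets a peer navigator, with a second contact at 2 to 4 weeks, so different dropout by arm is plausible. At stake is the estimated effect on the continuous survey scores (knowledge, self-efficacy, perceived benefit), which could be reported under an assurance that its analysis does not carry.

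**Working it through.** **1. The plan's own figures** (two-sided 0.05 assumed; sidedness is not stated).
- Dichotomous: 75 per arm, 23 points around 50%, so 38.5% v 61.5%. Power = Φ[(0.23√75 − 1.96√(2×0.5×0.5)) / √(2×0.385×0.615)] = Φ[(1.992 − 1.386)/0.688] = Φ(0.88) = 81.1%. The stated 80% is reproduced.
- Continuous: 60 per arm, 0.55 SD. Power = Φ[0.55/√(2/60) − 1.96] = Φ(3.01 − 1.96) = 85.4%. As a simple two-group comparison, the stated 80% is conservative.

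**2. Implied loss.** No loss rate is stated. From the power section, 1 − 60/75 = 20%. From the 80 per arm in the Hypotheses and Specific Aims section, 1 − 60/80 = 25%. The documents give both 75 and 80 per arm.

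**3. Bias by simulation.** From the plan: three visits (baseline, 3 and 6 months), 20% loss and CS 0.5. Assumed: Gaussian scores, a true 6-month arm difference of 0.50 SD, every correlation structure other than CS 0.5, and the dropout mechanism. In the main scenario 20% are missing at 6 months in each arm. In usual care, dropout depends on the 3-month score (log-odds −1 per SD); in the intervention arm it is random. There were 400,000 per arm, and repeat runs differ by about 0.01.

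| True correlations (0–3, 3–6, 0–6 months) | GEE, independence | GEE, exchangeable | Likelihood, unstructured |
|---|---|---|---|
| 0.5 / 0.5 / 0.5 (CS) | 0.42 (−16%) | 0.50 (0%) | 0.50 |
| 0.4 / 0.75 / 0.3 | 0.37 (−26%; unrounded 0.366, −27%) | 0.44 (−11%, unrounded) | 0.50 |

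Under two other structures (0.7/0.7/0.3 and 0.6/0.6/0.4), exchangeable GEE gave 0.48 to 0.49.

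- **Unequal rates** (30% v 10%, same dependence in both arms, CS): independence 0.42, likelihood 0.50.
- **Same mechanism and rate in both arms:** no bias for any method.
- **Other assumptions** (true 0.55 SD, dropout odds ratio 2 to 3 per SD, CS): independence GEE is off by −0.06 to −0.09 SD if only usual care is affected, and by +0.13 to +0.19 SD if the arms have opposite mechanisms. The sign can go either way.

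**4. Check by hand, and change scores.** Let d be the amount by which the mean 3-month score of retained usual-care women exceeds that of all usual-care women. Because dropout depends only on the 3-month score, the independence bias is −r(3,6)×d. CS gives d = 0.08/0.5 = 0.16; the second structure gives d = 0.13/0.75 = 0.17, which agrees. For complete-case change scores the bias is −[r(3,6) − r(0,3)]×d. That is −(0.5 − 0.5)×0.16 = 0 under CS, and −(0.75 − 0.40)×0.17 = −0.06 under the second structure (0.50 becomes 0.44). Change scores are therefore safe under CS but not in general.

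**5. Dichotomous outcomes, for illustration.** True difference 0.23, 20% loss depending on 3-month LARC use, with 3-month rates of 30% and 50% and a latent correlation of 0.8 assumed. Observed-data GEE with independence gave 0.235 to 0.289. Counting non-response as failure gave 0.187 to 0.232. The choice between them changes the answer, and the analysis text does not make it.

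**The case against.** A reader might infer that the plan claims MAR protection for GEE. It does not: the statement is attached to maximum likelihood techniques, used where appropriate and conditional on ignorable missingness, and for those models it is acceptable. The gap is that no such model is named.

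A reader might also infer that the LARC and clinic-visit results are at risk. The GEE sentence does sit with those outcomes, and both are dichotomous. However, the power section counts non-response as failure for them. If that rule is applied, GEE has no outcomes missing through dropout and the MAR weakness does not arise. Clinical records may also fill gaps when possible (section IV.B), and visit attendance during the study period reads as one indicator per woman. This objection stands, provided the rule is carried into the analysis, which the plan does not say.

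The sizes rest on assumed mechanisms, and an exchangeable working correlation under the plan's own CS 0.5 leaves almost no bias. This stands too, but the plan commits to neither structure for the analysis.

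The psychosocial item under Hypothesis 1 is worded for women who had a visit, not as a contrast of arms. Even so, section IV.G expects the trial to show the intervention's impact on knowledge.

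Finally, attrition checks are planned. They help with unequal rates and with baseline predictors. They would miss the main scenario above, where loss is 20% in both arms, and adjusting for baseline variables does not properly handle dropout driven by 3-month answers.

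**Conclusion.** The concern holds as a gap between an assurance and the analyses named. Its reach is the continuous survey scores, and the dichotomous outcomes only if non-response is not counted as failure. The possible bias in a 0.50 SD arm difference at 6 months was about 16% to 27% with independence GEE and 0% to 11% with exchangeable GEE.

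Those figures need dropout that depends on 3-month answers differently by arm, or that occurs at different rates by arm. The documents give no mechanism, so they show what could happen and do not forecast it. The conclusion that a planned 20% loss will bias the trial is not supported: the 20% is inferred (25% from 80 per arm), and equal dropout produced no bias. Likelihood models are themselves protected only under MAR. The change is worth making because a better-founded analysis is available at very little cost.

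**What to change.** - **Continuous scores (knowledge, self-efficacy, perceived benefit).** In place of GEE or change-score analysis, specify a likelihood-based mixed model with arm, visit, arm × visit, baseline included and unstructured covariance, using all randomised women with any data.
- **Dichotomous outcomes.** Keep GEE and state its working correlation. State in the analysis plan whether the power section's failure rule for non-response applies. If it does not, impute by arm from baseline and 3-month values (multiple imputation) before fitting GEE.
- **Missing-data paragraph.** The conditional statement about maximum likelihood can stay once it is tied to the named mixed model.

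Cost: SAP wording and slightly more programming in the SAS software already planned. No new data are needed.

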### *Study Condition*

*Usual Care.* All participants will be in active OMAT at one of the two clinics. The current standard of care is to administer the state mandates Infectious Disease Behavioral screen. If women screen at risk for HIV, they are referred to the Colorado department of Public Health and Environment or Denver Public Health for further evaluation and follow up. At this time, neither program has standard work in place to assess pregnancy desire, contraception use and/or to provide information on contraception methods or referral to services. Standard care varies depending on the length of time a patient has been in treatment, but all are connected to a counselor and a treatment provider. The intention of this study is not to impact the care provided in OMAT, but to support reproductive behaviors and connection to a family planning visit.

*Peer-Led Reproductive Health Intervention.* After randomization, if the participant is assigned to the study intervention condition the researcher will introduce them to the peer navigator (PN) immediately after the baseline interview. The timing of each session is listed in the table below followed by a short summary of core objectives of each session. The PN intervention is specified in the Peer Navigator Handbook included with this submission.

Intervention Components		
Session	Timing	Duration
Session I	Immediately post-baseline	15 minutes
Session II	2-4 weeks post-baseline	20 minutes

Session One: The PN will conduct session one as outlined in the Peer Navigator Handbook. Core objectives of this session include engaging the patient in the intervention, assessing pregnancy intentions and current behaviors, advising patients on birth control options and summarizing the session and preparing for next steps. Motivational interviewing techniques will be used throughout the sessions. The primary goal of the first session will be to assess interest and readiness to connect to a family planning provider and to schedule a same day appointment for those patients who are ready to take action. It is estimated to take approximately 15 minutes.

- **If the participant is interested** in connecting to a family planning visit: The PN will make an appointment with an identified health educator (HE). A HE is a Denver Health employee who specializes in family planning education. All attempts will be made to make the appointment on the same day as session one.

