#### **F. Data Analysis Plan:**

*Phase I Qualitative Data Analysis.* All qualitative data will be digitally recorded and in written notes. The tapes from the individual interviews will be transcribed (and translated when necessary), verbatim, directly after the interview. Coding will begin immediately and will be ongoing so that subsequent interviews can be used to clarify emerging themes.

Individual interviews that have been transcribed will be imported into ATLAS.ti for coding. A grounded theory approach will be used to inductively code and analyze the individual transcripts. Coding for the first 3 interviews will take place as a team (the PI and research assistant). The team will immerse themselves in these interviews starting with reading each interview transcription several times to begin to identify meaningful themes. The team will code the three interviews, labeling as many concepts as emerge, and meet to jointly develop and operationalize codes that will be used in coding subsequent interviews. The team will code the remaining interviews, meeting weekly to discuss problems or questions with current codes and make modifications as needed. Analysis will be an ongoing iterative process. Relevant themes/categories and topics will be extracted for use in the development of the intervention and focus group interview guide.

The intent of the focus groups is to provide feedback on the intervention developed. Therefore, the focus groups will be digitally recorded and reviewed after the group meeting. Notes from these groups will be summarized and the intervention will be modified based on the findings. Following completion of the analysis and intervention development, the recordings will be destroyed.

*Phase II Quantitative Data Analysis.* Multivariate regressions will be performed to assess statistical differences between the intervention group and usual care group from baseline to follow-up with respect to:

**Hypothesis 1.** Participants randomized to the intervention will be more likely to follow-up with a family planning clinic visit.

- Participants with a family planning visit will show an increase in knowledge, self-efficacy, and perceived benefit of birth control.

**Hypothesis 2.** Participants randomized to the intervention will be more likely to initiate Long Acting Reversible Contraceptive (LARCS) methods.

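### Continuous scores: no time coding, main visit or baseline adjustment is fixed, and the only time pattern powered is linear; a baseline-adjusted categorical-visit analysis would be a cheap improvement

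*Combined protocol and SAP*

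**What the plan says.** For continuous outcomes, the Study Statistical Power paragraph (section IV.F) states: "a follow-up sample size of 60 per group will provide 80% power". It then names two targets. The first is worded "to detect a .55 SD difference between usual care and intervention patients". The alternative, which assumes compound symmetry and a within-subject correlation of .5, is worded "or a medium linear effect over time". No size is attached to the word medium, and the visit for the .55 SD difference is not named.

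Surveys are taken at baseline, 3 months and 6 months (section IV, Phase II). In the intervention table under Study Condition, the second and last scheduled session falls at "2-4 weeks post-baseline", so scheduled peer contact ends before the first follow-up.

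On analysis, section IV.F says: "Separate analyses will be conducted for each of the hypothesis to understand differential change over time". It names change scores, analysis of variance, regression and GEE for repeated measures. It does not say whether time is linear or categorical, which of the two follow-ups carries the comparison, or whether the baseline score is a covariate. For significance, "the per comparison error rate of .05 will be used to evaluate significance of the specific aims".

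**The concern.** The only time pattern that the power text names is a straight line. On this visit schedule a straight-line contrast rests on month 6 and takes little or nothing from month 3. Because scheduled contact ends by week 4, a score effect could be present at month 3 and then hold or fade. If it fades, a linear contrast or month-6 change score has much less power than the plan's 80%.

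The second issue is freedom of choice. A slope, a month-3 change, a month-6 change and an average of the two follow-ups would each fit the analysis text as written. They estimate different things and have different power. With none named as the main one, a reader cannot tell which comparison the stated power refers to, and the choice could be made after the data are seen.

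**Working it through.** **Inputs from the documents.** 60 per group at follow-up; compound symmetry with rho = .5; alpha .05 per comparison; visits at 0, 3 and 6 months.

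**Assumptions.** Two-sided testing (the plan does not state sidedness), normal approximation, complete data, SD = 1 at each visit.

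**Step 1: the plan's own figure.** For a difference of .55 SD at one time point with 60 per group, SE = sqrt(2/60) = 0.183. Power = Phi(0.55/0.183 − 1.96) = 85% (t-test 84.8%), against the stated 80%. The difference detectable with 80% power is 2.80 × 0.183 = 0.51 SD (0.52 by t-test). The plan's .55 is therefore slightly conservative, and that is not the issue here. The linear alternative cannot be reproduced exactly because it has no number. Read as 0.5 SD more change by month 6, it gives 78%.

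**Step 2: weights of a linear contrast.** Centred visit times are −3, 0, +3. With complete data, compound symmetry and a free baseline difference, the slope weights are proportional to −1, 0, +1. The test is the month-6-minus-baseline change, and month 3 has no weight.

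**Step 3: variance per participant (SD squared), rho = .5.**
- Linear contrast or month-6 change: 2(1 − rho) = 1.00
- Baseline-adjusted month 6: 1 − rho² = 0.75
- Baseline-adjusted mean of months 3 and 6: (1 + rho)/2 − rho² = 0.50

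**Step 4: detectable difference and power.** SE = sqrt(2v/60), giving 0.183, 0.158 and 0.129. Detectable difference = 2.80 × SE. Power = Phi(effect/SE − 1.96). The effect is the month-6 value for the first two contrasts and the mean of both follow-ups for the third.

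| True effect (month 3, month 6) | Linear / month-6 change | Adjusted month 6 | Adjusted mean of 3 and 6 |
|---|---|---|---|
| Detectable at 80% (sustained effect) | 0.51 SD | 0.44 SD | 0.36 SD |
| Sustained (0.5, 0.5) | 78% | 89% | 97% |
| 25% fade (0.5, 0.375) | 54% | 66% | 92% |
| 50% fade (0.5, 0.25) | 28% | 35% | 83% |
| Truly linear (0.275, 0.55) | 85% | 94% | 89% |

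Example, 50% fade: the linear contrast has 0.25/0.183 − 1.96 = −0.59, so 28%. The adjusted mean has 0.375/0.129 − 1.96 = 0.94, so 83%.

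**Step 5: how far the result depends on the conditions.** The linear contrast loses half of its 78% only when the month-6 effect is below about 61% of the month-3 effect. If 20% miss month 6 only (75 falling to 60 per group), a likelihood-based slope gives month 3 a weight of about 0.11 against 0.95 for month 6. If the arms are constrained to be equal at baseline, the weights are 0.18 and 0.91, and power under a 50% fade is 53%.

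**The case against.** A reader might infer that the trial plans a linear-trend test that ignores the 3-month data and loses most of its power. The documents do not support that, for four reasons.

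- **No trend test is planned.** The linear effect is the second of two alternatives in the power text. The analysis section never specifies a slope, and its phrase about differential change over time says nothing about linearity. What stands is that time coding, visit and baseline handling are left open.
- **Zero weight for month 3 is conditional.** It needs complete data and a free baseline. The plan itself implies 20% loss (75 to 60 per group) and allows maximum likelihood where appropriate, so month 3 could carry some weight, though little.
- **The loss depends on a fade that the documents neither predict nor exclude.** Session two may lead to a new family planning appointment, and the one stated prediction for the scores concerns women who had such a visit. Effects could therefore build after week 4. A sustained effect keeps 78%, and a 25% fade keeps 54%.
- **Two changes are combined in the gain.** Adjusted month 6 alone reaches 89% for a sustained effect, so about half of the rise from 78% to 97% comes from baseline adjustment and not from using month 3. Averaging or naming month 6 is partly a choice of estimand, and durability at 6 months is a legitimate target.

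The scores are also not the headline outcomes. Hypothesis 1 ("Participants randomized to the intervention will be more likely to follow-up with a family planning clinic visit") and Hypothesis 2 (LARC initiation) are dichotomous.

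All four points stand. They narrow the claim but leave the recommendation intact, because the recommended analysis does not depend on a prediction of fading.

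**Conclusion.** This is a cheap improvement for the continuous scores only. The plan leaves their time effect, main visit and baseline handling unspecified, and the one pattern that it powers is linear and has no number. Under the plan's own 60 per group and rho = .5, both baseline-adjusted contrasts have more power than the linear contrast or month-6 change score in every scenario shown, including a truly linear effect (89% or 94% against 85%). The gain is largest if the effect fades: 83% against 28% for a half fade with the adjusted mean.

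These figures assume two-sided .05, complete data and compound symmetry. The 0.5 SD effect and the fade patterns are illustrations, not figures from the documents.

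**What to change.** In section IV.F, for the continuous scores:

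1. Replace change scores or a linear trend with a repeated-measures model of the 3- and 6-month values. Use visit as a categorical factor, arm by visit, and the baseline score as a covariate. The GEE already planned can carry this.
2. Prespecify one main contrast. One option is the baseline-adjusted mean of months 3 and 6 (detectable 0.36 SD). If durability is the target, use baseline-adjusted month 6 (detectable 0.44 SD).
3. Report the arm difference at both visits, whichever contrast is chosen.
4. In the power paragraph, replace the medium linear effect with the detectable difference for the chosen contrast, and state sidedness.

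The cost is wording in the analysis and power sections, with no new data or visits. The downside is small: if the effect truly grows in a line, the average has somewhat less power than adjusted month 6 (89% against 94%). Adjusted month 6 gives up much more if the effect fades by half (35% against 83%).
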